## SECTION I: RESEARCH PLAN

1. **Statement of Purpose:** State the scientific aim(s) of the study, or the hypotheses to be tested.

The specific aims of Sub-study #1 are:

Specific Aim #1: DEVELOPMENT: We will update our current Invite Only VR prototype into a polished videogame intervention using input from 4 focus groups of 5 adolescents each (n = 20), aged 12-17 and the extant literature. These focus groups will inform the development of the VR videogame intervention, *Invite Only VR*, for e-cigarette prevention among teens.

Specific Aim #2: EVALUATION: Conduct a pilot randomized controlled trial with 300 teens ages 11-15 comparing the Invite Only VR intervention vs. an attention/control non-health-related VR videogame, collecting assessment data at baseline, post-gameplay, three months and six months to determine:

- a. the preliminary impact of the intervention on knowledge, intentions, perceptions, attitudes, social norms, self-efficacy and behaviors related to: i) initiation of e-cigarette use, ii) e-cigarette use cessation.
- b. the intervention's acceptability and feasibility by collecting quantitative and qualitative data on teens' satisfaction and gameplay experience of the intervention.
- c. preliminary evidence of the impact of *Invite Only VR* on players' perception and experience of social pressure and social norm development.

The specific aim for Sub-study #2 is

Specific Aim #1: EVALUATION: Conduct a quasi-experimental effectiveness trial of the Invite Only VR intervention using a pre-post study design with 400 teens ages 11-15, collecting assessment data at baseline and post-gameplay to determine:

- a. the preliminary impact of the intervention on knowledge, intentions, perceptions, attitudes, social norms, self-efficacy and behaviors related to: i) initiation of e-cigarette use, ii) e-cigarette use cessation.
- b. the intervention's acceptability and feasibility by collecting quantitative on teens' satisfaction and gameplay experience of the intervention.

2. **Probable Duration of Project:** State the expected duration of the project, including all follow-up and data analysis activities.

2 years

3. **Background:** Describe the background information that led to the plan for this project. Provide references to support the expectation of obtaining useful scientific data.

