|  Decisionally Impaired |  Employees                         |  Pregnant women and/or fetuses           |
|  Yale Students         |  Females of childbearing potential |                                                                  |

NOTE: Is this research proposal designed to enroll children who are wards of the state as potential subjects?

Yes  No

8. **Inclusion/Exclusion Criteria:** What are the criteria used to determine subject inclusion or exclusion?

For the focus groups and pilot-testing, inclusion/exclusion criteria are: participants must be 12-17 years of age and speak English. For the randomized controlled trial, participants must be between the ages of 11-15, Speak English, and be able to play a mobile app-based videogame and VR videogame (willing to sit with a smartphone or tablet computer and/or use a VR headset for 45-60 minutes/session to play the game). Eligibility will be determined by the research team.

9. How will **eligibility** be determined, and by whom?

Eligibility will be determined by the research team. If a prospective participant meets the inclusion criteria, they will be eligible to participate in the project.

10. **Risks:** Describe the reasonably foreseeable risks, including risks to subject privacy, discomforts, or inconveniences associated with subjects participating in the research.

The potential risks associated with this study have to do with maintenance of the confidentiality of the identities of the participants enrolled in the study and information relating to them. De-identified hard copies of the data will be stored in locked cabinets and electronic data will be stored in secure, password-protected computers. Only the P.I. and other relevant research staff will have access to the data.

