Playing *Invite Only VR* may pose a potential psychological risk in that we address sensitive issues around tobacco use and its consequences. Research staff will be available to provide assistance to the participants, answer their questions, and serve as a resource if any distress or concern arises. The assessments and instruments may also present a potential risk given that some of the questions are sensitive in nature and address issues around substance use. Again, the Research staff will be available to assist the participants, the program sites staff, and the research staff members administering the assessments if there appears to be any distress around the questions being asked. If participants need additional or more intensive attention, [name] will provide consultation to the participant.

Also the use of a virtual reality headset for the project may pose a slight physical risks for the participants in the form of dizziness, queasiness, seizures (about 1 in 4000 experience this effect), eye or muscle twitching, and faintness.

11. **Minimizing Risks:** Describe the manner in which the above-mentioned risks will be minimized.

A number of precautions will be actively integrated into the research procedures to protect the confidentiality and anonymity of all participants. All research staff and the staff and volunteers participating in the intervention will be required to complete training in research ethics. Data collection forms will be designated by ID numbers only. A separate master file of names, addresses, contact persons, and telephone numbers, along with the study ID numbers will be maintained in a locked file cabinet in the P.I.'s research offices. All data entry and analyses will be completed with ID numbers only. The study will be explained to others, such as the guardian/parent and program staff as a study of child development that will focus on promoting healthy behaviors. In instances in which data are requested from other sources or it is beneficial to the participant to provide information to another individual or agency (e.g. medical personnel) this will only be done with the written permission of the guardian/parent on a "Release of Information" form stipulating

who the information is provided to, or received from. The research staff will follow standard confidentiality procedures for research programs.

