To minimize possible physical risks associated with the project, per the health and safety manual for the virtual reality headsets, participants will not be allowed to use the virtual reality headsets while they are tired, sleep impaired, if they have digestive problems, are under emotional stress or anxiety or suffering from a cold, flu, headache, migraine or earache. Additionally, participants using the virtual reality headsets will be required to take a 10-15 min break for every 30 mins of game play.

Furthermore, throughout their gameplay experience, to help minimize risk participants utilizing the VR headsets will be asked about how they are physically feeling. If the participant's answer indicates that they are experiencing any of the adverse physical symptoms, the research staff will immediately stop gameplay.

In the unlikely event that a participant involved with the study experiences a serious medical or psychological complication, that requires further attention, this would be reported to [name] who will then determine if further consultation is required without divulging the name of the individual, if this appeared appropriate and necessary. [name] would then be responsible for ensuring that the needs of the individual were addressed.

12. **Data and Safety Monitoring Plan:** Include an appropriate Data and Safety Monitoring Plan (DSMP) based on the investigator's risk assessment stated below. (Note: the HIC will make the final determination of the risk to subjects.)
- a. What is the investigator's assessment of the overall risk level for subjects participating in this study? Minimal risk
  - b. If children are involved, what is the investigator's assessment of the overall risk level for the children participating in this study? Minimal risk
  - c. Include an appropriate Data and Safety Monitoring Plan. Examples of DSMPs are available here <http://your.yale.edu/policies-procedures/forms/420-fr-01-data-and-safety-monitoring-plans-templates> for
    - i. Minimal risk
    - ii. Greater than minimal

The principal investigator is responsible for monitoring the data, assuring protocol compliance, and conducting the safety reviews quarterly. During the review process, the principal investigator will evaluate whether the study should continue unchanged, require modification/amendment, or close to enrollment.

The principal investigator or the Human Investigative Committee (HIC) have the authority to stop or suspend the study or require modifications.

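### Seizures are a named headset risk, but the written eligibility rule states no seizure-history exclusion and so would admit a child with known epilepsy

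*Combined protocol and SAP*

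**What the plan says.** All items below are in Section I of the combined protocol and SAP unless stated otherwise.

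- **Item 10 (Risks)** describes the physical risk of the headset as slight and lists "dizziness, queasiness, seizures (about 1 in 4000 experience this effect), eye or muscle twitching, and faintness".
- **Item 8 (Inclusion/Exclusion Criteria)** says that for the randomised trial "participants must be between the ages of 11-15, Speak English, and be able to play a mobile app-based videogame and VR videogame". A parenthesis explains ability as willingness to sit and use the device for a session. Focus groups and pilot-testing need only age 12-17 and English. No health exclusion is listed for anyone, and sub-study #2 is not mentioned.
- **Item 9 (Eligibility)** says "Eligibility will be determined by the research team" and continues "If a prospective participant meets the inclusion criteria, they will be eligible to participate in the project".
- **Item 11 (Minimizing Risks)** sets rules for headset use, given as "per the health and safety manual for the virtual reality headsets". They begin "participants will not be allowed to use the virtual reality headsets while they are tired, sleep impaired, if they have digestive problems" and go on to emotional stress or anxiety, cold, flu, headache, migraine and earache. Breaks are required. If a participant's answers show that they "are experiencing any of the adverse physical symptoms, the research staff will immediately stop gameplay".
- **Items 1 and 4, sub-study #2**, describe a study "using a pre-post study design with 400 teens ages 11-15" in the Seattle School District. All 400 play the game on a headset, and enrolment is by opt-out.

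**The concern.** The protocol identifies seizures as a foreseeable effect of the device, yet its entry rule would let in a child already known to have them. The visible safeguards apply on the day of the session or after symptoms have been reported. None of them is written to identify such a child before the headset goes on.

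What is at stake is the safety of minors. The point does not touch the estimand, the comparison between arms or the precision of any result.

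**Working it through.** No design figure is at issue, so the check is to apply the written rules to one hypothetical child: aged 13, English-speaking, willing to play, with diagnosed epilepsy.

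**Randomised trial**

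1. Item 8, age 11-15: met.
2. Item 8, speaks English: met.
3. Item 8, able to play, explained as willing to sit with the device: met.
4. Item 8, health exclusion: none listed.
5. Item 9: meeting the inclusion criteria is sufficient, so the child is eligible.
6. Item 11, conditions that bar headset use: none of those listed names epilepsy or seizure history. On a day when the child is rested, calm and free of the listed complaints, the list does not bar use.
7. Item 11, stop rule: this depends on the child's answers once play has begun, so it cannot screen beforehand.

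**Pilot-testing.** Age and English only (item 8). Steps 4 to 7 apply unchanged to any pilot-tester who wears a headset.

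**Sub-study #2.** Item 8 gives no criteria. The limits found elsewhere are age 11-15 (items 1 and 4), the Seattle School District (item 4) and English (Section III, item 8). None concerns health. No step described for this sub-study asks a parent about seizures. The stop rule assigns the action to research staff, but the team's described contact with classes is by video call, and school partners are the ones told to give breaks.

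**Size.** The number of avoidable seizures would be

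n × p × r,

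where n is the number of headset users, p is the proportion with a seizure history who would otherwise be admitted, and r is the headset seizure risk in those children. The documents give neither p nor r, so the product cannot be evaluated.

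The one rate that is given, 1 in 4000, is an overall rate. Read as a risk per participant, it gives for sub-study #2:

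- expected seizures: 400 / 4000 = 0.10
- chance of at least one: 1 − (3999/4000)^400 = 0.095

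These figures are background for all 400 users. They do not show what part of that risk an exclusion would remove.

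**The case against.** **Unseen documents.** A seizure warning or question would normally sit on the parent consent form or in the parent letter, and item 11 defers to a headset manual. None of these was available. This stands: a reader might infer that the study has no seizure screen at all, and the documents do not support that. They show only that item 8 neither states an exclusion nor points to one held elsewhere.

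**Higher risk in known epilepsy.** Item 10 gives a single overall rate and does not say who is at greater risk. This also stands. The step from a named hazard to excluding children with a seizure history is a clinical assumption and should be labelled as one.

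**Room for judgement.** The research team determines eligibility, item 4 says screening data are collected in sub-study #1, and the Healthy box is ticked in item 7. These point to a population of healthy children. However, the tick is an undefined recruitment category, the only criteria listed to screen against are those in item 8, and item 9 makes those criteria sufficient. This softens the point without removing it.

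**Eligibility is not headset use.** Item 11 is a separate bar applied before play, and its list includes migraine, which can recur, so it is not purely a list of passing states. That is fair, but nothing on the list names seizures.

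**Conclusion.** The point holds as a gap in the written rule and should be corrected. Items 8 and 9, followed literally, admit a child with known epilepsy, and the item 11 rules as listed do not keep that child off the headset. The gap is wider in sub-study #2, which has no criteria in item 8 and enrols by opt-out.

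The conclusion about the text rests on the protocol alone. The case for acting on it rests on two further assumptions: that a seizure history raises headset risk, and that the unseen forms and manual do not already screen for it.

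A reader might try to size the harm by counting headset users, for example 400 + 115 = 515 (sub-study #2 plus the stated intervention arm), or by applying the 1 in 4000 rate to such a count. Neither is supported. A count of those who would be asked is not a count of those protected, and this one leaves out any pilot-testers. The overall rate says nothing about the risk in the excluded children. No figure for avoidable risk can be given.

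**What to change.** 1. **Item 8:** add an exclusion for known seizures or epilepsy. State that it applies to every headset user in pilot-testing, the randomised trial and sub-study #2.
2. **Item 11:** add the same bar to the list of conditions that prevent headset use.
3. **Sub-study #1:** ask about seizure history on both the paper and the Qualtrics parent consent forms. Do so before randomisation, so that the exclusion falls equally on both arms and creates no post-randomisation withdrawals.
4. **Sub-study #2:** state the exclusion in the parent letter and the follow-up email, and repeat it in the classroom video briefing before any headset use. Name one opt-out contact. At present Section I, item 4 and Section III, item 3 direct parents to school program staff, while Section III, item 6 directs them to the PI.
5. **If the forms or the manual already contain the screen:** state the exclusion in item 8 and cross-reference them.

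The cost is one protocol amendment, small edits to documents already going to families, and a few children not enrolled (the documents do not allow a number). In sub-study #2 the check remains imperfect: under opt-out, a child stays enrolled unless a parent or the pupil responds.

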Tobacco use, including the use of e-cigarettes, is the leading cause of preventable disease and death in the United States and is linked to cancer and cardiovascular diseases. In 2016, 3.9 million middle/high school students used at least one tobacco product in the past 30 days and approximately 45% of middle/high school students used two or more tobacco products in the past 30 days. Of particular interest, e-cigarettes have emerged as an introductory tobacco product among youth due, in part, to their appealing flavors and perception that they are safer than other products. Given more than 80% of adult smokers begin using tobacco products such as e-cigarettes before the age of 18, there is a

need to develop interventions that will help prevent e-cigarette experimentation among young adolescents; a population inherently vulnerable to tobacco initiation and the development of life-long tobacco use.

The use of virtual reality (VR) has emerged as an effective intervention approach to addressing a range of health issues, including phobias, social anxiety, post-traumatic stress disorder and pain management. Currently, no research exists on the efficacy of evidence-based VR videogames related to tobacco use prevention.

4. **Research Plan:** Summarize the study design and research procedures using non-technical language that can be readily understood by someone outside the discipline. **Be sure to distinguish between standard of care vs. research procedures when applicable, and include any flowcharts of visits specifying their individual times and lengths.** Describe the setting in which the research will take place.

The goal of this research study is to conduct a randomized controlled trial of the VR-based e-cigarette prevention intervention, *Invite Only VR*, with the aim to prevent the initiation of e-cigarette use in teens by increasing their knowledge, decreasing their intentions to use e-cigarettes, influencing their harm perceptions and attitudes associated with e-cigarettes, and increasing behavioral skills associated with refusing peers involving e-cigarettes. *Invite Only VR* is an innovative, immersive intervention that may hold the promise to reducing e-cigarette initiation in teens.

For Sub-study #1:

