**Measures.** We will collect data on participant demographics at baseline. At baseline and immediately after gameplay, and again at 3 and 6 months post gameplay, we will collect data on intentions to initiate smoking, self-efficacy for refusing offers of e-cigarettes and other tobacco products, perceived social norms related to smoking, attitudes about smoking, and smoking behavior using validated questionnaires. Finally, we will assess satisfaction with game play and acceptability and feasibility of the intervention by collecting self-report data at the end of the game play period. All assessments will be conducted via face-to-face interviews with a research assistant and each adolescent.

**Study locations.** For the focus groups and pilot-testing, the study will take place at one of the after-school programs with which the play2PREVENT Lab has ongoing partnerships including but not limited to: Wilbur Cross High School (which serves 1300 students from 9th to 12th grade), Hamden Youth Center (which serves roughly 75 adolescents in the 6th through 12th grade, and the Milford Middle School District (which serves 1300 students the majority of whom are between the ages of 11 and 14), and LEAP (which serves over 1000 children between the ages of 7-18). For the randomized controlled trial, we will enroll students from the Milford Middle School District between the ages of 11-15.

**Participants, screening, and consent.** In collaboration with community program staff, we will discuss the study with interested parents and adolescents and collect eligibility screening data. If the participant is eligible and interested we will proceed with the consent procedures that will differ by phase of the research. For focus groups, we will give information sheets to the adolescents and to their parents describing the purpose of and protocol for the focus groups. Parents who do not wish for their children to participate will contact the project director. No forms will be signed for focus groups. For the randomized controlled trial, we will obtain written, informed assent (adolescent) and consent (parent).

In addition to paper forms for parental consent for participation in the randomized controlled study, we will also provide a web-based form for parents to review and electronically sign through Yale Qualtrics.

For Sub-study #2:

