Statistical procedures and models for analyzing data have been selected according to the research hypotheses being investigated and the types of data available. In general, we will use two-tailed tests and p-values smaller than 0.05 will be considered to indicate statistical significance. When necessary, however, we will use appropriate adjustment of the level of significance (alpha) to account for multiple statistical tests. All statistical analyses will be conducted on an intention-to-treat sample using either SPSS/SAS statistical packages. Baseline characteristics will be analyzed using descriptive statistics.

We will evaluate the efficacy of Invite Only VR at reducing initiation of e-cigarette use (primary outcome). We will test the hypothesis that individuals who play Invite Only VR will be less likely to report the initiation of e-cigarette use in comparison to the control condition. We will conduct a longitudinal analysis using a linear mixed models approach to compare participants in the intervention group to participants in the control group on e-cigarette use from baseline across all follow-up assessments. An advantage of mixed models is that participants with missing data need not be excluded as all available data are used in estimating parameters. We will also use logistic regression models to determine if any relevant baseline variables are associated with rates of initiation of e-cigarette use (constructed as a binary outcome (Yes/No). We plan to evaluate the prognostic significance of a small set of predictor variables (e.g., knowledge, intentions, perceptions, attitudes, social norms, and self efficacy) and use them as covariates in the primary analysis.

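### The primary outcome is initiation, but the stated arm comparison is a linear mixed model of e-cigarette use whose variable, at-risk group and contrast are undefined

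*Combined protocol and SAP*

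**What the plan says.** All analysis statements are in Section I, item 13 (Statistical Considerations). It makes initiation of e-cigarette use the primary outcome and hypothesises that "individuals who play Invite Only VR will be less likely to report the initiation of e-cigarette use" than controls. The comparison of arms follows: "We will conduct a longitudinal analysis using a linear mixed models approach to compare participants in the intervention group to participants in the control group". The outcome of that model is described no further than this: "on e-cigarette use from baseline across all follow-up assessments". The reason given for this model is the handling of incomplete follow-up: "An advantage of mixed models is that participants with missing data need not be excluded as all available data are used in estimating parameters".

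The next sentence reads: "We will also use logistic regression models to determine if any relevant baseline variables are associated with rates of initiation of e-cigarette use". Only here is initiation given a Yes/No coding, and no arm term is mentioned. Predictors found this way are then to serve as covariates in the primary analysis, which is not identified by model. On population: "All statistical analyses will be conducted on an intention-to-treat sample".

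Elsewhere in Section I:
- Item 4 describes the intervention "with the aim to prevent the initiation of e-cigarette use in teens". Its Measures paragraph collects smoking behaviour "At baseline and immediately after gameplay, and again at 3 and 6 months post gameplay".
- Item 8 sets randomised-trial eligibility by age, English and ability to play. Never-use at baseline is not required.
- Item 1, Specific Aim #2 of Sub-study #1, lists cessation beside initiation.

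**The concern.** Initiation is a one-way event that only a never-user can have. Use over time, measured in everyone, is a different quantity unless it is coded and contrasted so that it reduces to initiation. The plan does not say that it is. No section defines an at-risk group, says how repeated reports become an initiation event, or names the model term that tests the hypothesis.

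Two things are at stake. The primary test may answer a question other than the one posed. And the choices that decide this (coding, contrast, covariance) stay open until the data have been seen, although item 13 sets a two-sided 0.05 threshold for an efficacy hypothesis.

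**Working it through.** The documents give no initiation, baseline-use, quitting or dropout rate and no power figure, so there is nothing to reproduce. All rates below are assumptions for illustration. The 115 per arm is from the randomised-trial paragraph of item 4; an equal split of the 300 enrolment target would be 150 per arm. Data are complete and no covariates are used unless stated.

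**1. Use coded as current use.** Suppose 10% are users at baseline, initiation is identical in both arms, and quitting differs by 30 points. The arm difference in use is 0.10 x 0.30 = 0.03, or 3 points. At 20% baseline users it is 0.20 x 0.30 = 0.06. Neither reflects initiation.

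**2. Use coded as ever-use, no true effect.** Assume 10% baseline ever-users and cumulative initiation among never-users of 0.5%, 5% and 10% at post-gameplay, 3 and 6 months. As shares of all participants these are 0.45%, 4.5% and 9.0%.
- The change between two visits has variance d(1-d), where d is the share newly reporting use between them. The six visit pairs give 0.00448, 0.04298, 0.08190, 0.03886, 0.07819 and 0.04298; mean 0.04823.
- A random-intercept model gives every pair the same variance, so its month-6 standard error is sqrt(2 x 0.04823/115) = 0.02896.
- The true standard deviation of that contrast is sqrt(2 x 0.08190/115) = 0.03774.
- False-positive rate: 2[1 - Φ(1.96 x 0.02896/0.03774)] = 2[1 - Φ(1.504)] = 13.3%, against a nominal 5%.

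Simulation over 5-20% initiation, at 115 or 150 per arm, gave 12.1-14.5% for this contrast. It gave 4.4-5.3% for an arm main effect and 3.9-5.2% for the 6-month change with its own variance.

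**3. Use coded as ever-use, true effect.** Assume cumulative initiation of 0.5%, 8%, 15% (control) and 0.2%, 2.7%, 5% (intervention), with 10% baseline ever-users.
- *Arm main effect over all four visits.* A baseline ever-user has a person-mean of 1. A first report at post-gameplay, month 3 or month 6 gives 0.75, 0.50 or 0.25.
  - Control mean: 0.10 + 0.9(0.005 x 0.75 + 0.075 x 0.50 + 0.07 x 0.25) = 0.1529.
  - Intervention mean: 0.10 + 0.9(0.002 x 0.75 + 0.025 x 0.50 + 0.023 x 0.25) = 0.1178.
  - Difference 0.0351. The variances (mean square minus squared mean) are 0.1000 and 0.0941, so SE = sqrt(0.1941/115) = 0.0411 and z = 0.85. Power = Φ(0.85 - 1.96) + Φ(-0.85 - 1.96) = 14%.
- *6-month change with its own variance.* Difference 0.9 x 0.10 = 0.09; SE = sqrt((0.135 x 0.865 + 0.045 x 0.955)/115) = 0.0373; z = 2.41; power about 68% (simulation 69%).
- *6-month comparison in never-users.* 0.9 x 115 = 103.5 per arm; SE = sqrt((0.15 x 0.85 + 0.05 x 0.95)/103.5) = 0.0411; z = 2.43; power 68% (simulation 68%).

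**4. Sensitivity (simulated power, 115 per arm).**

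| Baseline ever-use | Arm main effect | 6-month change, own variance | Never-users at 6 months |
|---|---|---|---|
| 0% | 68% | 74% | 74% |
| 2% | 37% | 73% | 72% |
| 10% | 14% | 69% | 68% |
| 20% | 9% | 64% | 64% |

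At 150 per arm and 10% ever-use, the main effect has 17% and the other two 80-81%.

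**The case against.** The mixed-model sentence directly follows the initiation hypothesis, so its authors may have used e-cigarette use as shorthand for initiation. Carrying predictors of initiation into the primary analysis points the same way. This stands: a reader might infer that the plan contains no between-arm test of initiation at all, and the text does not establish that.

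A reader might also infer that a linear model, or the inclusion of baseline users, is wrong in itself. It is not. A 6-month change with its own variance matches the never-user comparison in step 3. The wording about change from baseline fits that contrast better than a main effect averaging in baseline, so the 14% power belongs to the less natural choice. Likewise, the 13-14% error rate belongs to one contrast under one covariance: a joint arm-by-time test under the same random-intercept model gave 6.8-8.9%, still inflated but much less.

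Nor is a survival model essential. With missing visits simulated (115 per arm, 10% ever-use), a discrete-time survival model and a plain comparison of never-users counting any earlier report both had 61.5% power. A random-intercept model with robust standard errors had 57.5%.

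The trial is also called a pilot with preliminary aims. That lowers the stakes, but item 13 still states a primary outcome, an efficacy hypothesis and a significance threshold. None of these points supplies the missing variable, at-risk group or contrast. The smoking-behaviour measure cites a timeline follow-back reference, which does not settle the coding either.

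**Conclusion.** The point holds as a mismatch between outcome, hypothesis and stated model, and should be fixed before outcome data are examined. Read as current use, the test mixes initiation with quitting. Read as ever-use, the same sentence permits a sound analysis, one with a false-positive rate near 13-14%, or one with about 14% power where 68-69% was available.

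These sizes rest wholly on assumed rates, complete data and no covariates. With no baseline users the power gap nearly closes (68% against 74%), but the random-intercept error rate does not depend on baseline users. The documents do not support the claim that the trial will have these error rates, only that the plan does not rule them out.

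**What to change.** In Section I, item 13:

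1. Define the primary endpoint as first reported e-cigarette use by 6 months among participants reporting never-use at baseline, analysed as randomised. State that this is the at-risk subset of the intention-to-treat sample.
2. Name one prespecified binary model with an arm term as the primary analysis. Discrete-time (pooled logistic) survival over the follow-up visits keeps all available data, which is the plan's own reason for mixed models. Logistic regression of initiation by 6 months, counting any earlier report, is also acceptable.
3. Report the 6-month risk difference with a 95% confidence interval.
4. State in advance whether any planned baseline covariates enter, and which, limited to what the expected events can support. With 207 never-users (0.9 x 230), 10% initiation gives about 21 events and 5% about 10, against six candidate predictors listed.
5. Keep the linear mixed model as secondary in all participants, naming its variable and 6-month contrast and using robust standard errors. An unstructured covariance is risky: if 0.5% of never-users initiate by post-gameplay, the chance that nobody has done so is 0.995^207 = 35%. Baseline and post-gameplay ever-use are then identical and the covariance is singular.

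Costs: a protocol modification; an e-cigarette ever-use item at each visit, if the smoking-behaviour measure does not already supply it; and the loss of baseline ever-users from the primary contrast (about 23 of 230, or 30 of 300, at 10%). The change does not make the trial well powered: for 10% versus 5% initiation, a direct comparison of 115 per arm has about 30% power.
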